1.4.4 Temozolomide

Temozolomide (Temodar®) is an alkylating drug indicated for the treatment of adult patients with newly diagnosed glioblastoma multiforme (GBM) concomitantly with radiotherapy and then as maintenance treatment.

The most common adverse reactions (≥10% incidence) reported for temozolomide include: alopecia, fatigue, nausea, vomiting, headache, constipation, anorexia, convulsions, rash, hemiparesis, diarrhea, asthenia, fever, dizziness, coordination abnormal, viral infection, amnesia, and insomnia.

The most common Grade 3 to 4 hematologic laboratory abnormalities (≥10% incidence) that have developed during treatment with temozolomide are: lymphopenia, thrombocytopenia, neutropenia, and leukopenia.

Allergic reactions have also been reported.

Please refer to the Physician Desk References and package insert for complete information.

Temozolomide is part of the standard of care for glioblastoma and the patient and/or patient's insurance carrier will be responsible for charges related to its administration and for medications that may be needed to prevent or control side effects.

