1.8.2 Clinical Data

The literature provides several immunotherapy trials that incorporate wild type survivin peptides as target antigens and show the induction of specific T-cell activity in a limited number of patients with advanced solid tumors (32-35). A phase II trial (36) in 61 HLA-A1/-A2/-B35-positive, metastatic melanoma patients, using survivin-targeted peptide vaccination demonstrated prolonged OS in 13/41 patients who exhibited survivin-specific T-cell reactivity (SSTR) (median 19.6 vs 8.6 months; p=0.0077). It also revealed that the induction of SSTR was associated with gender and disease stage, rather than age, HLA type, performance status or vaccination regimen. It was observed that the majority of treatment-related side effects were mild to moderate (CTC grade 1-2), including fever, chills on the day of vaccination and inflammatory reactions at the

injection sites. The occurrence of these post-vaccination inflammatory reactions was strongly associated with the presence of SSTR and a trend toward favorable survival.

SVN53-67/M57-KLH has been studied in a phase I clinical trial sponsored and conducted by Roswell Park Cancer Institute. In that trial, nine patients with recurrent, survivin-positive malignant gliomas who had failed standard therapy, received SVN53-67/M57-KLH [(500 mcg) in Montanide ISA 51 with sargramostim (100 mcg)] subcutaneously at two-week intervals, for four doses, until tumor progression. In addition, patients who survived six months or more without tumor progression, serious adverse events, or regimen limiting toxicity received maintenance phase dosing every three months. Toxicity attributable to SVN53-67/M57-KLH was mostly limited to mild injection site reactions. SVN53-67/M57-KLH-Montanide-sargramostim was well tolerated and the majority of AE were grade one. Six of nine patients experienced injection site reactions, all grade one, including localized areas of erythema related to vaccination. Three patients reported fatigue (grades 1 and 2), two patients experienced myalgias (grade 2). Lymphopenia was seen in 3 patients (all grade 1) and leukopenia (grades 1 and 2) occurred in three patients. The only grade 3 AE, a seizure, was not related to the vaccine. One SAE (renal failure) occurred in the maintenance phase in one patient but was unrelated to the study drug.

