10.1.1.3 Abnormal Laboratory Values

Only clinically significant laboratory abnormalities that require active management will be recorded as AEs or SAEs on the CRF (e.g., abnormalities that require study drug dose modification, discontinuation of study treatment, more frequent follow-up assessments, further diagnostic investigation, etc.).

If the clinically significant laboratory abnormality is a sign of a disease or syndrome (e.g., alkaline phosphatase and bilirubin 5 x the upper limit of normal associated with cholecystitis), only the diagnosis (e.g., cholecystitis) needs to be recorded on the Adverse Event CRF.

If the clinically significant laboratory abnormality is not a sign of a disease or syndrome, the abnormality itself should be recorded as an AE or SAE on the CRF. If the laboratory abnormality can be characterized by a precise clinical term, the clinical term should be recorded as the AE or SAE. For example, an elevated serum potassium level of 7 mEq/L should be recorded as "hyperkalemia"

Observations of the same clinically significant laboratory abnormality from visit to visit should not be repeatedly recorded as AEs or SAEs on the CRF, unless their severity, seriousness, or etiology changes.

The following clinical laboratory tests will be performed during this study to assess safety (see Schedule of Procedures and Observations: **Table 3**, for specific tests):

- Hematology
- Serum Chemistries
- Urinalysis

The following evaluations will also be performed during the study to measure the safety and tolerability of study treatment:

- Vital sign measurements
- Physical examination
- Neurological examination
- Karnofsky Performance Status

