12.3 Study Endpoints

Primary Endpoint:

• PFS is defined as the time from date of diagnosis to the date of first observed disease progression or death due to any cause. All patients will be followed for a minimum of 6 months relative to evaluating the primary endpoint.

Secondary Endpoints:

- OS is defined as the time from date of diagnosis until date of death or the last date patient known alive (if death is not observed).
- Number of Grade 3 or 4 toxicities, according to National Cancer Institute Common Toxicity Criteria for Adverse Events (NCI CTCAEs) Version 4
- Immune responses to SurVaxM and predictors of response

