12.6 Safety Analysis

Safety and tolerability will be assessed by incidence, severity, and changes from baseline of all relevant parameters including adverse events (AEs) (see **Section 12.8**), laboratory values and vital signs.

Vital sign results (systolic and diastolic blood pressure, pulse, respiration, and temperature) will be summarized descriptively for each scheduled and unscheduled protocol time point. Changes will be calculated relative to the assessments at baseline.

The changes in hematology, chemistry, and other laboratory values will be summarized descriptively for each scheduled and unscheduled protocol assessment time point. Changes will be calculated relative to the values collected at baseline. Data listings of all laboratory data collected during the study will be presented. Laboratory values outside normal limits will be identified in data listings and will include flags for high and low values.

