Both objective tumor response rate (applicable only for patients with evaluable disease at study entry, as defined per RANO criteria) and toxicity rate (Grade 3 or Grade 4 toxicities, according to National Cancer Institute Common Toxicity Criteria for Adverse Events (NCI CTCAEs) Version 4) will be estimated using simple relative frequencies. The corresponding 95% confidence intervals for the estimated probabilities will be computed using the method proposed in Clopper and Pearson, 1934 ⁽⁴³⁾. The relationship between binary outcomes and collected demographic and baseline variables will be statistically assessed using logistic regression in an exploratory fashion. Maximum likelihood estimation will be utilized in the model fitting procedures as implemented by SAS PROC LOGISTIC. Wald tests of the model effects will be performed to assess statistical significance; see SAS documentation for details. See Hosmer and Lemeshow, 2000 ⁽⁴⁴⁾ for a discussion of such techniques. Alternative parametric models will be considered if model fit is found to be inadequate.

Objectives based on continuous outcomes such as immune response measured over time will be address in a similar fashion. A series of exploratory analyses will initially take place including individual subject-level profile plots and overall mean plots used to examining the mean structure. Formal statistical examination of longitudinal patterns will be done through the use of

a mixed model. Restricted maximum likelihood estimation will be utilized in the model fitting procedures as implemented by SAS PROC MIXED (version 9.2). Once the model is fit, specific linear contrasts based on the estimated model parameters will be constructed and used to test hypotheses concerning between time point comparisons. We acknowledge the possibility of informative missingness, that is, the probability of a particular observation being missing may be related to the health of the subject, and therefore analyses will be interpreted with caution.

All tests will be two-sided and tested at a 0.05 nominal significance level. Standard diagnostic plots will be used to assess model fit and transformations of variables may be considered in order to meet statistical assumptions.

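### Laboratory abnormalities become adverse events only if they need active management, so a Grade 3-4 toxicity rate built from AE records can miss severe laboratory values, chiefly lymphopenia and leukopenia

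*Combined protocol and SAP*

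**What the plan says.** - **Recording rule (10.1.1.3).** "Only clinically significant laboratory abnormalities that require active management will be recorded as AEs or SAEs on the CRF". The examples of active management are dose modification, stopping treatment, closer follow-up and further work-up, and the list is left open. CTCAE grade is not a criterion.
- **Endpoint (12.3).** "Number of Grade 3 or 4 toxicities, according to National Cancer Institute Common Toxicity Criteria for Adverse Events (NCI CTCAEs) Version 4". Laboratory toxicity is not excluded.
- **Estimator (12.7, secondary analyses).** The Grade 3-4 toxicity rate "will be estimated using simple relative frequencies", and "The corresponding 95% confidence intervals for the estimated probabilities will be computed using the method proposed in Clopper and Pearson".
- **Where grading applies.** Section 10.1.2 prescribes CTCAE v4 for AE reporting. Section 12.8 summarizes AEs by worst severity grade among patients who received at least one dose.
- **Laboratory analysis (12.6).** The opening sentence includes laboratory values among the parameters to be assessed for incidence and severity. The methods then given are descriptive changes from baseline and listings: "Laboratory values outside normal limits will be identified in data listings and will include flags for high and low values".
- **Expected toxicity (1.4.4).** "The most common Grade 3 to 4 hematologic laboratory abnormalities (≥10% incidence) that have developed during treatment with temozolomide are: lymphopenia, thrombocytopenia, neutropenia, and leukopenia".
- **AE definition (10.1.1).** An AE can be any unfavorable sign, abnormal laboratory findings included, with no requirement that action be taken.

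**The concern.** The endpoint is defined by severity, but laboratory events enter the AE record by whether someone acted on them. These are different tests. A Grade 4 lymphocyte count that leads to no intervention meets the endpoint definition and fails the recording rule. A milder abnormality that leads to a repeat blood draw can pass the recording rule.

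This is the only safety rate with a planned confidence interval. An exact interval describes sampling error and cannot reflect events that were never recorded. The omission would also depend on how readily each investigator acts on a count, so it could differ between centers. Section 12.10 gives rigorous CTCAE evaluation of both drugs as one reason for having no early-termination criteria, which puts weight on the completeness of the graded data. The counts also matter for the immune-response objective, because Section 2 cites a report linking temozolomide-induced leukopenia to a stronger response to another peptide vaccine.

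**Working it through.** The plan states no toxicity rate, threshold or toxicity-based sample size, so there is no figure of its own to reproduce. The check has two parts.

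**1. Which Grade 3-4 laboratory values could go unrecorded?**

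- *Neutrophils and platelets.* Section 6.2.2 and Table 2 give thresholds for delaying or reducing temozolomide. Values crossing them would normally count as managed and be recorded.
- *Chemistry.* Table 2 requires action for Grade 3 and Grade 4 non-hematological toxicity, so drug-related chemistry abnormalities during temozolomide would usually be recorded.
- *Lymphocytes and total leukocytes, cycle 1.* Section 6.1 makes the dose increase after cycle 1 conditional on no Grade 3 or 4 hematological toxicity. Table 1 makes the higher dose level conditional on no toxicity of Grade 3 or above. Read literally, severe lymphopenia in cycle 1 affects the dose and could be recorded for that reason.
- *Lymphocytes and total leukocytes, other periods.* Table 2 has no row for either. The SurVaxM hold in 6.2.1 covers unexpected toxicity plausibly associated with the vaccine or sargramostim, whereas 1.4.4 lists lymphopenia and leukopenia as common with temozolomide. No specific trigger is stated for priming, for later cycles once the dose is set, or for vaccine-only maintenance.

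Table 4 calls for every Grade 3-4 AE at any attribution, but only once the event has been classed as an AE, so it does not restore these values. The underlying data do exist: Table 3 schedules a blood count with differential at screening, at all four priming visits, at each temozolomide cycle and at maintenance visits.

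**2. How large could the effect be? (illustration only)**

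Assumptions not in the documents: 20% of patients have a recorded Grade 3-4 event, and a proportion p have an unrecorded Grade 3-4 lymphopenia or leukopenia. The 10% in 1.4.4 is the minimum incidence of each abnormality, not of abnormality needing no action, so it is not a floor for p. With N = 50 the reported rate is 10/50 = 20%, Clopper-Pearson 95% CI 10.0-33.7%.

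Complete patient-level rate:
- independent: 1 - (1 - 0.20)(1 - p)
- full overlap: the larger of 0.20 and p
- no overlap: 0.20 + p

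| p | Full overlap | Independent | No overlap |
|---|---|---|---|
| 10% | 20% | 28% | 30% |
| 20% | 20% | 36% | 40% |
| 30% | 30% | 44% | 50% |
| 40% | 40% | 52% | 60% |

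Under independence, 28% is 14/50 (95% CI 16.2-42.5%) and 52% is 26/50 (37.4-66.3%). The complete rate passes the reported upper limit when 1 - 0.80(1 - p) > 0.337, that is, when p > 1 - 0.663/0.80 = 0.171. With full overlap and p of 20% or less, the patient-level rate does not change at all.

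**The case against.** The strongest reply is that the plan does not say the Grade 3-4 rate comes from the AE form. That is correct: the link is an inference from 10.1.2 and 12.8. A statistician could grade the laboratory data directly and still comply with 12.3. Section 12.6 also opens by promising incidence and severity of laboratory values, so a severity analysis is not absent; what is missing is a method, since changes and high/low flags are not CTCAE grades.

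A reader might infer that severe lymphopenia triggers no action anywhere in the protocol, or that only neutrophils and platelets have action rules. The documents do not support either. The dose-increase condition in 6.1 and Table 1 is not limited to those two counts, Table 2 covers non-hematological toxicity, and 6.2.2 leaves room for investigator discretion. The examples of active management in 10.1.1.3 are broad enough for some investigators to record severe lymphopenia, so total loss should not be assumed.

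A reader might also infer that the phase I safety profile in 1.8.2, which reports Grade 1 lymphopenia in three of nine patients, was collected under a different rule. The phase I recording rule is not given and no formal comparison of toxicity rates is planned, so that cannot be claimed.

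It is also fair that no decision rule depends on this rate and that grading can be done late. Both points limit the consequence. Neither settles what the endpoint counts.

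**Conclusion.** The concern holds in a conditional form. If the Grade 3-4 rate is taken from AE records, the rule in 10.1.1.3 can omit laboratory toxicity that meets the endpoint definition, to a degree that depends on the investigator. The exposure is mainly lymphopenia and leukopenia in the periods without a stated trigger.

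The direction is known: downward or zero, never upward. The size is not. The range of 28% to 52% against a reported 20% depends on an assumed recorded rate, an assumed p and independence. Overlap is plausible, because patients with severe lymphopenia on an alkylating drug may also have recorded neutropenia or thrombocytopenia, and it would shrink the gap. The illustration should not be read as an estimate for this trial.

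The plan should be changed because the endpoint's source is unstated, 10.1.1 and 10.1.1.3 disagree on what counts as an AE, and the remedy uses data already scheduled for collection.

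**What to change.** 1. In 12.3, 12.6 and 12.7, name the data source and state that hematology and chemistry values are graded by CTCAE v4 directly from the laboratory data.
2. Count treatment-emergent laboratory toxicity in the Grade 3-4 rate, defined as Grade 3-4 and worse than the patient's baseline grade. The baseline condition is needed: eligibility sets no lymphocyte limit and patients enter after chemoradiation, so a raw worst post-baseline grade would count lymphopenia that was already present. It also matches 10.1.1.4, which records a preexisting condition only if it worsens.
3. Report the rate with and without laboratory-only events, each with its Clopper-Pearson interval.
4. Add a shift table from baseline grade to worst post-baseline grade.
5. Reconcile the AE definition in 10.1.1 with 10.1.1.3. The 10.1.1.3 rule may stay for CRF entry.

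The cost is some programming and a short amendment to the statistical section, with no new visits or samples. The drawback is that the headline toxicity rate is likely to look less favorable.

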10.1.1.4 Preexisting Medical Conditions (Baseline Signs and Symptoms)

A preexisting medical condition should be recorded as an AE or SAE only if the frequency, severity, or character of the condition worsens during the study. When recording such events on an Adverse Event CRF, it is important to convey the concept that the preexisting condition has changed by including applicable descriptors (e.g., "more frequent headaches").

10.1.2 Grading and Relationship to Drug

The descriptions and grading scales found in the CTEP Version 4 of the NCI Common Terminology Criteria for Adverse Events (CTCAE) will be utilized for AE reporting. CTEP Version 4 of the CTCAE is identified and located at:

http://ctep.cancer.gov/protocolDevelopment/electronic applications/ctc.htm.

AEs not covered by specific terminology listed should be reported with common medical terminology, and documented according to the grading scales provided in the CTCAE Version 4.

The relationship of event to study drug will be documented by the Investigator as follows:

- **Unrelated:** The event is clearly related to other factors such as the participant's clinical state, other therapeutic interventions or concomitant drugs administered to the participant.
- **Unlikely:** The event is doubtfully related to investigational agent(s). The event was most likely related to other factors such as the participant's clinical state, other therapeutic interventions, or concomitant drugs.
- **Possible:** The event follows a reasonable temporal sequence from the time of drug administration, but could have been produced by other factors such as the participant's clinical state, other therapeutic interventions or concomitant drugs.
- **Probable:** The event follows a reasonable temporal sequence from the time of drug administration, and follows a known response pattern to the study drug. The event cannot be reasonably explained by other factors such as the participant's clinical state, therapeutic interventions or concomitant drugs.
- **Definite:** The event follows a reasonable temporal sequence from the time of drug administration, follows a known response pattern to the study drug, cannot be reasonably explained by other factors such as the participant's condition, therapeutic interventions or concomitant drugs; AND occurs immediately following study drug administration, improves upon stopping the drug, or reappears on re-exposure.

	10.1.2.1 S	everity assess	ment of Ini	ection Site	Reaction
--	------------	----------------	-------------	-------------	----------

Adverse Event	Grade 1	Grade 2	Grade 3	Grade 4	Grade 5
Injection Site Reaction	Tenderness with or without associated symptoms (e.g., warmth, erythema, itching)	Pain; lipodystrophy; edema; phlebitis	Ulceration or necrosis; severe tissue damage; operative intervention indicated	Life-threatening consequences; urgent intervention indicated	Death
Acneiform or Papulopustular Rash	Papules and/or pustules covering <10% BSA, which may or may not be associated with symptoms of pruritus or tenderness	Papules and/or pustules covering 10-30% BSA, which may or may not be associated with symptoms of pruritus or tenderness; associated with psychosocial impact; limiting instrumental ADL	Papules and/or pustules covering >30% BSA, which may or may not be associated with symptoms of pruritus or tenderness; limiting self care ADL; associated with local superinfection with oral antibiotics indicated	Papules and/or pustules covering any % BSA, which may or may not be associated with symptoms of pruritus or tenderness and are associated with extensive superinfection with IV antibiotics indicated; life-threatening consequences	Death
Maculo-papular rash	Macules/papules covering <10% BSA with or without symptoms (e.g., pruritus, burning, tightness)	Macules/papules covering 10-30% BSA with or without symptoms (e.g., pruritus, burning, tightness); limiting instrumental ADL	Macules/papules covering >30% BSA with or without associated symptoms; limiting self care ADL		
Pustular rash		Localized; local intervention indicated (e.g., topical antibiotic, antifungal, or antiviral)	IV antibiotic, antifungal, or antiviral intervention indicated; radiologic or operative		
Pain	Mild pain	Moderate pain; limiting instrumental ADL	Severe pain; limiting self care ADL		
Induration	Mild induration, able to move skin parallel to plane (sliding) and perpendicular to skin (pinching up)	Moderate induration, able to slide skin, unable to pinch skin; limiting instrumental ADL	Severe induration, unable to slide or pinch skin; limiting joint movement or orifice (e.g., mouth, anus); limiting self care ADL	Generalized; associated with signs or symptoms of impaired breathing or feeding	Death

BSA = Body Surface Area

ADL = Activities of daily living.

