1.4 Study Drugs

1.4.1 SVN53-67/M57-KLH (SurVaxM)

1.4.1.1 Peptide selection for SurVaxM

The survivin peptide in SurVaxM is a defined, 15 amino acid antigenic peptide capable of binding several human MHC class I molecules, as well as murine H2-Kb molecules (as a model of the human response). SurVaxM contains a core epitope SVN56-64/M57 modified by substitution of methionine for cysteine at amino acid position 57, with flanking amino acids 53-56 and 65-67. This allows the core epitope in SurVaxM to be more immunogenic than the wild-type survivin peptide in humans since it binds HLA-A*02 molecules to a much greater extent (16). While SurVaxM was designed to bind HLA-A*0201, computer algorithms predict its binding to numerous MHC class I molecules (including HLA-A*02, HLA-A*03, HLA-A*11 and HLA-A*24) that collectively represent a large patient population. Thus, SurVaxM is predicted to be effective at generating CTL in a diverse patient population with limited HLA restriction.

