12.8 Adverse Event

AEs will be coded using the latest available version of the Medical Dictionary for Regulatory Activities (MedDRA). AEs will be summarized for each treatment arm by the number and percentage of patients who experienced the event, according to system organ class and preferred term. Additional summaries will also be provided by severity grade and relationship to study drug, and for SAEs and events resulting in the permanent discontinuation of therapy. A patient reporting multiple cases of the same AE will be counted once within each system organ class and similarly counted once within each preferred term, and adverse events will be graded by worst severity grade. Unless specified otherwise, the denominator for these calculations will be based on the number of patients in each treatment arm who receive at least one dose of study drug, irrespective of the total number of doses administered. All participants who receive any study treatment will be considered evaluable for toxicity.

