12.10 Interim Analysis and Criteria for Early Termination of the Study

There are no planned interim analyses (unless for safety reasons) or early termination criteria based on the following:

- 1. The completed phase I trial of SVN53-67/M57-KLH showed very little toxicity with no grade III or IV adverse events and no serious adverse events attributable to the study drug.
- 2. There is no scientific rationale to posit additive or synergistic toxicity between the two drugs, given that one is an alkylating agent and the other is a vaccine.

- 3. In three separate trials (ACTIVATE⁽³⁸⁾, ACT II⁽³⁹⁾ and ACT III⁽³⁷⁾), rindopepimut (an immunotherapy for the treatment of EGFRvIII-expressing GBM) given in combination with temozolomide showed no serious toxicity with only minor injection site reactions, similar to SVN53-67/M57-KLH.
- 4. In addition to evaluation of immune responses and PFS, the current phase II design includes rigorous evaluation of toxicity of each drug with CTCAEv4.0 (see **Sections 6.2.1** and **6.2.2**).

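### Adverse events are attributed once to an undefined *study drug*, so vaccine and temozolomide toxicity may be mixed in the related-event tables and low-grade events captured unevenly

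*Combined protocol and SAP*

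**What the plan says.** Section 10.1.2 sets a five-level scale with one rating per event: "The relationship of event to study drug will be documented by the Investigator as follows". No section defines *study drug*. Within the scale, the definition of Unlikely switches to investigational agent(s). An event rated Possible is one that "could have been produced by other factors such as the participant's clinical state, other therapeutic interventions or concomitant drugs".

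The documents place temozolomide on both sides. It is subsection 1.4.4 under the heading "1.4 Study Drugs", beside SurVaxM, Montanide and sargramostim, and it is subsection 7.3 under Investigational Products. Yet 1.4.4 and 7.3 describe it as standard of care, and 7.3 adds that the study does not supply it.

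The rating is used in two places. Table 4 (10.1.3) requires Grade 1-2 events to be reported only if rated Possible or higher, and Grade 3-4 events at every rating. Section 12.8 says: "Additional summaries will also be provided by severity grade and relationship to study drug". The Grade 3-4 toxicity rate, under Secondary Analyses in 12.7, has a Clopper-Pearson interval and no split by agent.

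Section 12.10 gives four reasons for having no planned interim analysis (other than for safety) and no early termination criteria. The fourth is that "the current phase II design includes rigorous evaluation of toxicity of each drug with CTCAEv4.0", with a reference to Sections 6.2.1 and 6.2.2. Section 2 makes the same statement in support of going straight to phase II.

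**The concern.** The secondary safety objective (3.2) concerns SurVaxM in patients who are also receiving temozolomide. There is no control arm to show what temozolomide alone would produce, so the attribution rating carries much of the burden of telling the two apart.

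The toxicity profiles overlap. Section 1.4.4 names lymphopenia, thrombocytopenia, neutropenia and leukopenia under "The most common Grade 3 to 4 hematologic laboratory abnormalities", at an incidence of 10% or more. In the phase I vaccine trial (1.8.2), lymphopenia and leukopenia were each seen in 3 of 9 patients, at Grades 1-2, and three patients reported fatigue, which 1.4.4 also lists for temozolomide. A low count or fatigue rated Possible could therefore point to either treatment.

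If sites read *study drug* differently, the related-event tables cannot be interpreted as a vaccine safety profile. Low-grade events left unreported at some sites could not be recovered at analysis.

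**Working it through.** The plan gives no figure to reproduce here. The check is a comparison of passages, with two small calculations.

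**1. The two readings, applied to an event that the investigator believes temozolomide caused**

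| | Temozolomide is a study drug (1.4.4, 7.3) | Temozolomide is a concomitant drug |
|---|---|---|
| Rating under 10.1.2 | Probable or Definite | Unrelated or Unlikely |
| Grade 1-2, Table 4 | reported | not reported |
| Grade 3-4, Table 4 | reported | reported |
| 12.8 relationship table | related | not related |
| 12.7 Grade 3-4 rate | counted | counted |

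The reading changes what related means at every grade, and whether a Grade 1-2 event is reported. It does not change the Grade 3-4 rate.

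**2. Whether the cited sections supply per-drug evaluation.** The second reason in 12.10 speaks of two drugs, one an alkylating agent and the other a vaccine, so each drug in the fourth reason means temozolomide and SurVaxM. Section 6.2.1 asks whether an unexpected significant toxicity is reasonably likely to be associated with SurVaxM and/or sargramostim, in order to hold a dose. Section 6.2.2 adjusts temozolomide by counts and toxicity grade. Neither creates an attribution field for each adverse event or a summary by agent.

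**3. Whether dose timing separates the two.** The first vaccine dose falls 7-28 days after chemoradiation, with doses every 14 days (4.1, 6.1). The nominal dose days are therefore 7, 21, 35, 49 at the earliest and 28, 42, 56, 70 at the latest. With adjuvant temozolomide at its earliest permitted start:

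- Day 28 (4.1, 6.1): 2 or 0 of the 4 priming doses come before it.
- Day 42 (Table 3, footnote 2): 3 or 1 of the 4 come before it.

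Timing therefore separates the treatments only in part, and every dose follows six weeks of radiation with temozolomide. The 28-day and 42-day statements contradict each other and must be reconciled.

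**4. Size of the possible difference.** With no events, the Clopper-Pearson 95% upper limit is 1 − 0.025^(1/n).

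- n = 50: 1 − 0.025^(1/50) = 0.071, so 0-7%.
- n = 65: 1 − 0.025^(1/65) = 0.055, so 0-5.5%.

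The toxicity denominator lies somewhere up to 65. Section 12.8 counts everyone who receives any study treatment, and 12.1 allows up to 65 enrolled to reach 50 evaluable.

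For contrast, assume that 10-30% of patients have a Grade 3-4 event from temozolomide. At n = 50, 5 events give 10% (3-22%) and 15 events give 30% (18-45%). The planned all-cause rate would show these figures even if no event were vaccine-related.

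**The case against.** The strongest reply is that usage mostly points to SurVaxM. In the phase I account, *study drug* means the vaccine. Section 6.1.1 uses the term for vaccine injection sites. Section 1.4.3 says the vaccine, Montanide and sargramostim are provided free, whereas temozolomide is charged to the patient or insurer. The scale itself names concomitant drugs as an alternative cause. A site that reads it this way would separate the two. This stands as the likelier reading, but nothing instructs sites to adopt it. Usage is also uneven: 10.1.1.3 refers to modifying the dose of the study drug, while 6.2.1 allows no adjustment of the administered SurVaxM dose.

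A reader might infer that vaccine and temozolomide toxicity cannot be separated at all. The documents do not support that. Injection-site reactions have their own grading (10.1.2.1) and are measured after each vaccination (6.1.1). Events are tabulated by preferred term (12.8), all laboratory data are listed (12.6), and 6.2.1 requires a vaccine-specific judgement for a dose hold.

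A reader might also infer that severe events would be lost. They would not, because Table 4 takes all Grade 3-4 events. Even among Grade 1-2 laboratory findings, 10.1.1.3 admits only those that are clinically significant and need active management, which limits the exposure further.

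An all-cause Grade 3-4 rate is also a legitimate endpoint for the regimen. That is correct, and it should be kept. That this rate would be mostly temozolomide is plausible but not shown, since the 10-30% is assumed. Finally, the adverse event form is not among the documents and may already have a field for each agent. If so, the text needs only to be aligned with it.

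**Conclusion.** The point holds as a defect of definition with consequences for the safety data. The plan uses one attribution to an undefined term, and its own headings support two readings. Under the plan as written, the 12.8 relationship tables could mix vaccine and temozolomide attribution, and Grade 1-2 temozolomide events could be captured at some sites and not at others. The per-drug toxicity evaluation offered in Sections 2 and 12.10 is not provided by the sections they cite or by the planned analyses.

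The extent of any mixing is unknown. It depends on how sites read the term and on a form that the documents do not show. The numerical contrast, an all-cause rate of 10-30% against a vaccine-related rate of 0 with an upper limit of 5.5-7%, rests on an assumed temozolomide rate and on a denominator of 50 to 65. It illustrates the problem and is not a forecast. The primary PFS6 test is unaffected.

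**What to change.** - **10.1.2 and the adverse event form:** define *study drug*, and record the relationship separately for (a) the vaccine regimen, meaning SurVaxM/Montanide with sargramostim, and (b) temozolomide. A further split of sargramostim from SurVaxM would add little, because the two are injected at the same visit 1-3 cm apart and 6.2.1 already groups them.
- **Table 4:** state which attribution drives the Grade 1-2 filter.
- **12.7 and 12.8:** report the Grade 3-4 rate with its Clopper-Pearson interval twice, once regardless of cause and once as at least possibly related to the vaccine regimen. Use all patients who receive at least one SurVaxM dose (up to 65) as the denominator, and say so in 12.8. Give the relationship tables for each attribution.
- **Sections 2 and 12.10:** point the statement about each drug to these provisions.

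The cost is one extra attribution field per event, one extra table and, depending on the Table 4 choice, possibly more Grade 1-2 reports. Attribution remains a subjective judgement in an open-label trial, which is why the all-cause rate stays alongside.
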